**Table 1: Protocol Deviations Considered to be Violations**

Potential Violations	Detail/Criteria	Reason
Delayed or Incomplete treatment	Failure to treat within first 48 hours of diagnosis or receive less than 3 doses*	IMP needs to be taken within 48 hours of diagnosis and at least 4 doses are deemed necessary for clinical effectiveness
Mis- Dosing	Patient is given incorrect vials leading to 'mixed' treatments	May receive different treatment to the one assigned, or a combination of both treatments
Inclusion criteria	Failed one or more inclusion criterion	Data changed after dosing had commenced
Exclusion criteria	Failed one or more exclusion criteria	Data changed after dosing had commenced
Eligibility	Failed one or more eligibility criteria	Data changed after dosing had commenced
Temperature excursion	IMP must be stored at 2 – 8 °C**	Active ingredient may be affected by temperature excursion.
Other reasons	Any Major Deviation considered by the Sponsor and Medical Monitor that might influence the effectiveness of the active compound	To ensure that the PPS contains only subject data which has not been 'clinically' compromised. Reasons for this decision will be recorded in a comments column on the assignment population spreadsheet during the population assignment meeting.

\*Patients who die during the dosing period will not be excluded from the PPS.

\*\* Individual temperature deviations outside 2-8 may have been accepted and the IMP considered valid for use based on IMP stability data. Those patients who have received an IMP with a temperature excursion, but accepted by the Sponsor, are not classified as Protocol Violations.

**Consent:**

Full details of the consent procedures are given in Section 9.6 of the protocol. In summary, whenever possible informed consent will be obtained from the patient. When this is not immediately possible due to the patient's condition, the informed consent can be given by a:

PerLR: Personal Legal Representative (e.g. relative, partner or close friend)

PrfLR: Professional Legal Representative (e.g. doctor not involved in the study)

Note: A separate consent will also be requested for patient's genetic sampling.

After PerLR or PrfLR, Investigators will attempt to obtain retrospective consent until Day 360, unless the patient's condition has precluded this (e.g. in case of death). If the patient refuses to give retrospective consent and the reason for withdrawal is 'retrospective consent not given' then all data for this patient will be removed from any analyses population group.

Withdrawal of consent: Patients may withdraw or be withdrawn (by the PerLR or PrfLR) from the study at any time and, any data collected up to the time of withdrawal can be included, unless consent for any use of the data has also been withdrawn. If not specified otherwise, data will be used up until the time of withdrawal.

Patient data excluded from any or all analysis populations because of a withdrawal of consent will also be reported in the population assignment record.

---

## **5. Study Methods**

The subject assessments performed during both the Short Term and Long Term/Extended Follow Up periods together with the timetable of events are summarised using only details relevant to the analyses provided. Precise details of all assessments performed on each study day are given in Section 6 of the protocol.

### ***5.1 Schedule***

The timetable of events are summarised in Table 2.

**Table 2 Study Timetable and Assessment Overview (See protocol for full details)**

Procedure	Screening period	Double-blind treatment period				Short-term follow-up until D28 or discharge from ICU (whichever is earlier)				Long-term follow-up			Extended follow-up	
		Baseline period	D1 pre-dose	D1	D2-D6	D7-D14	D7-D28		D15-D27	Last day in ICU b	D28 c	D90 d +14 days		D180 +14 days
Informed consent	X													
Medical history	X													
Demographic details	X													
Documentation of chest X-ray or CT scan	X													
Inclusion/exclusion criteria	X	X e												
Randomisation		X f												
Administration of study drug			X	X										
Survival				X	X									X
On mechanical ventilation? (Y/N)				X	X									X
In ICU/in hospital? (Y/N)				X	X									X
SOFA		X		X	X	X		D21	X	X				X o
GCS (for SOFA and APACHE II)	X	X	X	X	X	X		D21	X	X				X o
APACHE II	X g													
Renal and vasoactive support? (Y/N)		X		X	X	X								X

Procedure	Screening period	Double-blind treatment period Days 1-6				Short-term follow-up until D28 or discharge from ICU (whichever is earlier)				Long-term follow-up			Extended follow-up
		Baseline period	D1 pre-dose	D1	D2-D6	D7-D14	D15-D27	Last day in ICU b	D28 c	D90 d +14 days	D180 +14 days	D360 ±14 days	
Blood sample: IFN beta-1a neutralising antibodies		X h						X					
Blood sample: MxA		X h			X	X							
EQ-5D-3L, FEV 1 and 6MWT		EQ-5D-3L l									X		X
PaO 2 /FIO 2	X	X			X	X	X	X					
Blood sample: CD73 and PIM		X h			X	X							
Pharmacoeconomics													
Physical examination	X							X	X				
Vital signs	X i	X			X	X	X	X	X				
ECG		X				D7					X		X
Haematology, chemistry, urinalysis k	X l	X			X	X	X	X	X		X o		
Pregnancy test in women of childbearing potential	X												
Previous and concomitant medications and therapies	X l	X											
Adverse events	X m	X									X n	X n	X n
Blood sample: genetic analysis (requires separate consent)	X												

a No more than 48 hours may elapse between confirmation of moderate or severe ARDS and administration of the first dose of study drug.

b These assessments will be done on the day the patient leaves the ICU, which will either be on D28 or earlier, according to the clinical progress of the patient. If the patient is still in the ICU on D28, the next visit or telephone contact will be at D90. If a patient leaves the ICU before D28, the survival status and other endpoints must be assessed on D28.

c D28 procedures apply for patients leaving the ICU before D28 and for patients withdrawing from the study before D28. For patients withdrawing from the study before D28 a sample should be taken for neutralising antibodies on the day they leave the ICU.

d D90 can either be a visit or telephone contact.

e Reconfirm inclusion/exclusion criteria before dosing, including that patient requires mechanical ventilation and is in the ICU (patients requiring ECMO after randomisation but before the first dose of IMP may still be included).

f Randomise after consent obtained and once eligibility criteria confirmed.

g Within 24 hours of ICU admission

h Within 1 hour pre-dose.

i Baseline EQ-5D-3L to be obtained from relatives and checked later with patient.

j For APACHE II scoring.

k Samples should be taken in the morning between 04:00 and 10:00.

l Medicines and therapies in previous month.

m Adverse events will be recorded after informed consent is obtained.

n Deaths are reported as SAE

o If it is possible to be performed by the investigator

Abbreviations: APACHE II=Acute Physiology and Chronic Health Evaluation; CD=cluster of differentiation; CT=computerised tomography; D=study day; ECG=electrocardiogram; ECMO=extra-corporeal membrane oxygenation; EQ-5D-3L=EuroQol 5-Dimensions 3-Level questionnaire; FEV1=forced expiratory volume in 1 second; GCS=Glasgow Coma Scale; ICU=intensive care unit; IFN=interferon; MxA=myxovirus resistance protein A; PaO2/FiO2=partial pressure of oxygen/fraction of inspired oxygen; PM=potential inflammatory marker; SOFA=Sequential Organ Failure Assessment; 6MWT=6-minute walk test;.

## ***5.2 Patient Status And Baseline Characteristic Assessments Prior To Treatment Start***

Study specific patient eligibility assessments required prior to recruitment are recorded during Screening and/or at Pre-Dosing on Day 1 (Baseline).

### ***5.2.1 Admission***

At Admission to the ICU they include details of: Status including Intubation, Renal support, Body position and any required Vasoactive infused drug treatment.

These are then supported by a combined assessment of Acute physiology and Chronic health to derive an APACHE II score (0-71) to additionally classify the severity of the condition.

Demographics (Age, Race, Sex) are then supplemented with details of the Disease diagnosis and Aetiology supported by Imaging (Chest X-ray / CT scan) and Ventilation evidence (Gas exchange variables). Aetiology is categorised as: Pancreatitis, Trauma/Burns, Sepsis, Multiple Transfusion, Aspiration, Pneumonia or Other. If the cause is Sepsis then the site of infection is noted.

Following satisfactory completion of all the Inclusion/Exclusion criteria details (including a negative pregnancy test for females) Medical history (including any relevant previous and ongoing medical conditions) is recorded together with Prior medications (taken in the last 30 days but stopped before signing Informed consent) and a complete Physical examination (with predicted body weight).

Ongoing medications are recorded as Concomitant Medications (classified as either Bolus or Infusion) and reported accordingly if started prior to treatment dosing (Day 1). Any medication given with or after the first injection of study drug is also classified as a concomitant treatment.

Prior to the start of dosing on Day 1 the Patient status and Inclusion/Exclusion criteria are confirmed and all Medications are updated.

A series of Baseline safety assessments are then performed. These include: Safety laboratory tests (Biochemistry, Haematology, Urinalysis), Vital signs, 12 Lead ECG and Ventilation (Gas exchange). Specific variables measured are listed in section 5.8.

Baseline efficacy assessments performed are: the System Organ Failure SOFA score and Quality of Life (EQ-5D-3L) assessment. Details of the specific variable items measured are given in section 5.3.3.5 and 5.4.2 respectively.

Pre-dose blood samples are taken for pharmacodynamic baseline assessment. These include: Myxovirus Resistance Protein A (MxA), CD 73 biomarker, Potential Inflammatory Markers (PIMs). Also a sample for Anti Drug Antibodies (ADA) and Neutralising Antibodies (NABs) to Interferon Beta-1a assessment will be taken. A tier based approach for the NABs analyses will be used where NABs will be assessed only if ADAs exists.

If all the study specific inclusion criteria are met then the patient is eligible for entry into the study. Screen failures are retained in the database, but only the patient screening number and reason for exclusion will be listed in the report.

### **5.2.2 Randomisation**

Randomisation details, including details of the severity of the ARDS condition and any change in the condition are recorded on Day 1 of dosing. Drug compliance is not measured but a record of the daily infusion of the Study IMP (material number, date and time of administration) is maintained on Days 1-6. These data will be categorically summarised and individual details listed. Details of the construction (including block size) and application of the randomisation will be described in the Statistical Report. The severity of ARDS reported at Day 1 dosing will be used to assign patients to their respective groups (i.e. Moderate or Severe), irrespective of the stratification selected in the IWRS system.

### **5.3 Efficacy Assessments - Short Term Follow Up**

Daily assessments are performed in the ICU for the evaluation of treatment benefit. This is the Short Term Follow Up period (Day 1 to Day 28).

Efficacy related assessments are predominantly performed as part of the Patient Status evaluation (see Section 5.3.1).

From these observations both primary and secondary efficacy endpoints to the end of the Short Term Follow Up period Day 28 can be derived. They include: Mortality (All causes), Mortality in ICU, Mortality in hospital, Days free of organ failure, of renal support, of vasoactive support and of mechanical ventilation together with the Number of ICU care free days and the Number of days in hospital. A combination of Mortality and the Need for mechanical ventilation is used to determine the primary efficacy outcome of the treatment (see Section 5.3.2).

Further efficacy evaluations involve assessment of the impact on body organs as a whole through the Sequential Organ Failure Assessment (SOFA) and individually through the need for Vasoactive support, Ventilation performance and Fluid balance and these are recorded separately (see Section 5.3.3).

The end of the Short Term Follow Up may be less than Day 28 if the patient is Discharged from the ICU or Withdrawn from the study. In either event a complete set of assessments identical to those performed daily and at the conclusion of the Short Term Follow Up (Day 28).

Further assessments following discharge from the ICU are then performed at Long Term and Extended Follow Up on Day 90 and Day 180 and Day 360 respectively (see Section 5.4).

#### **5.3.1 Patient Status Assessments**

The Patient Status assessments are performed on Days 1 (Pre-dose) then daily on Days 2 - 28 (Day 28 In or Out of ICU). At each visit patient details recorded are: Alive/Dead, Location of

death (ICU/Hospital), Date of death, Location if alive (ICU/Hospital), Requirement for mechanical ventilation, On renal support and Relative change in condition from yesterday.

At selected visits (Day 1 (Pre-dose), Day 27 - 28), Body positioning (except Day 28 if already left ICU), Vasoactive support and Concomitant medications and Other therapies are recorded.

Prior to Day 28 in the event of withdrawal an Early Termination is completed. In the event of discharge from the ICU a Last Day in ICU form is completed. Each includes a complete set of Patient Status evaluations.

In addition, at Day 28 patients who have been externally transferred and are no longer in the ICU complete details of the Total number of days spent free of Mechanical ventilation, free of Organ failure (SOFA score=0), free of Renal support and free of Vasoactive support. Totals for the entire short term follow up period are derived (see Section 5.9.4, Appendix 4). In addition, the total number of days spent in the ICU and the Hospital environment are also similarly derived.

### ***5.3.2 Primary Efficacy - Ventilation Free Survival (VFDsurv)***

The primary endpoint for treatment benefit includes Mortality and the Number of days free of Mechanical ventilation within 28 days among survivors as a composite measure (VFDsurv).

Mortality is patient death by Day 28. Ventilator-free days (VFDs) correspond to those days when unassisted breathing (UAB) is possible for a complete calendar day. For the initiation of the VFD count at least two consecutive calendar days of UAB are required.

The definition of UAB is given in the protocol and the actual VFDsurv and VFD scoring mechanisms are described in Section 5.9.4, Appendix 4.

### ***5.3.3. Secondary Efficacy***

Secondary efficacy assessments include: Mortality (All causes), Mortality in ICU, Mortality in hospital, Days free of Organ failure, of Renal support, of Vasoactive support and of Mechanical ventilation together with the Number of ICU care free days and the Number of days in hospital.

Additionally, Organ failure (SOFA score) and individual organ assessment through Vasoactive support, Ventilation performance and Fluid balance are also assessed.

#### ***5.3.3.1 Mortality Evaluations***

Mortality is primarily assessed in the hospital at Day 28. All details are obtained from the daily assessment of Patient Status. Mortality is categorised as: Mortality (All causes), Mortality in ICU and Mortality in hospital.

The Mortality rate will be a proportion derived from the number of deaths up to Day 28 divided by the total number of eligible patients in the FAS patient population. The Mortality rate in the

ICU and Mortality rate in the hospital will be similarly calculated based on the location of the death.

Investigators are required to confirm mortality using the 'Death report' section of the eCRF. In the event of missing or insufficient information then patients are assumed alive and still 'at risk' at the time of assessment.

### ***5.3.3.2 Days Free Of Mechanical Ventilation Evaluations***

The Total number of days free of Mechanical ventilation is derived from the Patient Status report recorded on each day during the 28 day period. Patients who die during this period will be assigned a value of zero. Defined rules are specified in Section 5.9.4, Appendix 4.

The definition used by site staff for unassisted breathing (UAB) and 'being ventilator free for the whole of the calendar day' as recorded in the CRF is given in the protocol.

This variable is not the same as the calculated Ventilation Free Days (VFD) endpoint which contributes to the VFDsurv primary efficacy endpoint as it requires 2 consecutive calendar days of UAB. If there are fewer than 2 consecutive days of UAB then VFD is assigned the value zero.

### ***5.3.3.3. Days Free Of Organ Failure, Renal Support, Vasoactive Support Evaluations***

Patient assessment of Organ failure, Renal support and Vasoactive support is also recorded daily in the Patient Status record.

The Number of days free of Organ failure, Renal support and Vasoactive support is derived from this information using defined rules and algorithms specified in Section 5.9.4. Patients who die during this period will be assigned a value of zero.

A patient will be defined as being free of organ failure when the SOFA score is zero. However, as organ failure is only assessed at Day 21 and Day 28 after Day 14 a scoring scheme will be used to derive the total number of days.

This is:

If Day 21 and Day 28 are both zero then 50% of the days between Day 14 and Day 21 and 100% of the days between Day 21 and Day 28 will be assumed to be zero.

If Day 21 is non-zero and Day 28 is zero then 100% of the days between Day 14 and Day 21 will be assumed to be non-zero and 50% of the days between Day 21 and Day 28 will be assumed to be zero.

Finally if Day 21 is zero and Day 28 is non-zero then 50% of the days between Day 14 and Day 21 will be assumed to be zero and 100% of the days between Day 21 and Day 28 will be assumed to be non-zero (also see Section 5.9.4.2, Appendix 4).

The need for Renal support or for Vasoactive support is defined in the protocol.

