#### 6.1.2 Secondary Efficacy Variables

##### 6.1.2.1 Sequential Organ Failure Assessment

Organ failure status will be assessed using the SOFA score, which assesses six organ systems: respiration, coagulation, liver, cardiovascular, central nervous system and

renal (Table 2). (Ref: Grissom et al 2010) A patient will be defined as being free of organ failure when the SOFA score is zero. The score will be assessed pre-dose on D1 and daily up to D14, at D21 and at D28 while the patient is in the ICU, based on worst daily values.

The SOFA score variables to be assessed daily from baseline to D28/leaving the ICU are:

- PaO2/FiO2 (mmHg)
- Platelets × 10^3/mm^3
- Bilirubin (µmol/L or mg/dL)
- Hypotension/use of vasopressors
- Glasgow Coma Scale (GCS)
- Creatinine (µmol/L or mg/dL)

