#### *8.5.2.2 Days Free of Organ Failure, Renal Support, Vasoactive Support, ICU Care and Days in Hospital*

Organ failure-free days are defined as the number of days in the first 28 days after the first dose of study drug that the patient is alive and free of organ failure with a SOFA score of zero.

ICU-free days are defined as the number of days from the time of ICU discharge to D28, assuming survival for at least two consecutive calendar days after ICU discharge and continued stay outside the ICU setting to D28. If a patient returns to the ICU and subsequently needs ICU admission to D28, ICU-free days will be counted from the end of the last period of ICU discharge to D28. A period of ICU admission lasting less than 24 hours in relation to a surgical procedure will not count in the calculation of ICU-free days. If a patient was in the ICU at D27 or dies prior to D28, ICU-free days will be zero. Patients transferred to another hospital or healthcare facility will be followed to D28 to assess this endpoint.

The statistical methods to be used for these secondary efficacy endpoints will be detailed in the SAP.

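### The fill-in rule for organ-failure-free days does not use the D14 SOFA score, so a patient with SOFA 0 at both D14 and D21 is credited only half of that interval

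*SAP*

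**What the plan says.** Protocol 8.5.2.2 counts the days in the first 28 "that the patient is alive and free of organ failure with a SOFA score of zero". Protocol 6.1.2.1 schedules the score "daily up to D14, at D21 and at D28 while the patient is in the ICU". SAP 5.3.3.3 gives the gap in that schedule as its reason for filling in: "as organ failure is only assessed at Day 21 and Day 28 after Day 14 a scoring scheme will be used".

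Three cases follow, each defined by D21 and D28 alone:

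- **D21 zero, D28 zero.** First interval: "If Day 21 and Day 28 are both zero then 50% of the days between Day 14 and Day 21" are taken as free. Second interval: "100% of the days between Day 21 and Day 28 will be assumed to be zero".
- **D21 non-zero, D28 zero.** First interval: "100% of the days between Day 14 and Day 21 will be assumed to be non-zero". Second interval: "50% of the days between Day 21 and Day 28 will be assumed to be zero".
- **D21 zero, D28 non-zero.** The first interval again gets half ("if Day 21 is zero and Day 28 is non-zero then 50% of the days between Day 14 and Day 21"), and the second gets nothing.

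The case with D21 and D28 both non-zero is not written out. The section refers to Section 5.9.4.2 of Appendix 4, which is not in the text available for this review.

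The resulting total is analysed with the van Elteren test (SAP 6.2.4.3, by reference to 6.2.4.2). It also enters the cost derivation as 28 minus days free (SAP 5.5).

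**The concern.** D14 opens the first interval and its SOFA score is already collected, yet no case depends on it. In effect the rule treats every patient as having organ failure at D14. For a patient who did not, it contradicts itself: an interval that starts and ends at zero earns full credit in the fourth week but half credit in the third.

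At stake is the accuracy of a tested secondary endpoint for patients already free of organ failure by D14. Each uncounted day also becomes a day of organ-failure support in the cost calculation. SAP 5.9.6 otherwise plans no imputation, so this exception ought to be coherent.

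**Working it through.** The plan states no day count for this rule, so there is no figure to reproduce. The check lists what the rule credits and compares it with a rule that uses the scores at both ends of an interval.

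**Inputs.** The credits come from SAP 5.3.3.3 and the schedule from Protocol 6.1.2.1. Let L be the number of days in an interval. Strictly between assessments, L = 6 (D15–D20 and D22–D27). Counting one end as well, L = 7. The SAP does not say which it means, so both are shown.

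**Step 1: the rule's own logic, from D21 to D28**

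| D21 | D28 | Credit | L = 6 | L = 7 |
|---|---|---|---|---|
| 0 | 0 | 100% | 6 | 7 |
| non-zero | 0 | 50% | 3 | 3.5 |
| 0 | non-zero | 0% | 0 | 0 |
| non-zero | non-zero | not stated | – | – |

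**Step 2: D14 to D21, rule as written against both-ends credit** (100% if both are zero, 50% if exactly one is, 0% if neither)

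| D14 | D21 | SAP, L = 6 | Both ends, L = 6 | Difference (L = 6; L = 7) |
|---|---|---|---|---|
| 0 | 0 | 3 | 6 | −3; −3.5 |
| non-zero | 0 | 3 | 3 | 0; 0 |
| 0 | non-zero | 0 | 3 | −3; −3.5 |
| non-zero | non-zero | 0 | 0 | 0; 0 |

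The two rows with D21 non-zero rest on the stated case with D28 = 0. For D28 non-zero, a credit of 0 is assumed.

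Rows 2 and 4, where D14 is non-zero, agree exactly. Row 1 is the internal contradiction: 0.5 × 6 = 3 days, where the identical pattern in Step 1 earns 6. Row 3 is different in kind. Its 0% differs from the 50% convention but matches what Step 1 gives a relapse, so it is a matter of convention.

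**Step 3: group level, illustrative only.** Let p be the share of patients with SOFA 0 at both D14 and D21 whose total is not set to zero by death. The mean undercount from row 1 is 3p (L = 6) or 3.5p (L = 7). The documents give no p. Assuming 2% to 30%:

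- L = 6: 3 × 0.02 = 0.06 to 3 × 0.30 = 0.9 days
- L = 7: 3.5 × 0.02 = 0.07 to 3.5 × 0.30 = 1.05 days

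If p differed between arms by an assumed 5 to 15 percentage points, the difference in means would shift by 0.15 to 0.45 days (L = 6) or 0.18 to 0.53 days (L = 7).

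**Step 4: cost.** Under SAP 5.5, days of use are 28 minus days free. A 3-day undercount therefore adds 3 × the daily organ-failure unit cost for that patient. Unit costs are still to be confirmed in SAP Table 4, so no amount can be given.

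**The case against.** **The governing derivation may lie elsewhere.** SAP 5.3.3.3 defers to Appendix 4, Section 5.9.4.2, which cannot be checked here and may contain a D14 condition. This stands as a limit. Even so, the body text as written would then disagree with the appendix and need alignment.

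**True status on unscored days is unknown.** Undercount can therefore only mean inconsistent with the rule's own treatment of a zero-to-zero interval. That is accepted, and it is why the figure rests on row 1 alone.

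**Few patients may be affected.** SOFA 0 needs normal values in all six systems (Protocol Table 2), and the D14 and D21 scores are taken in the ICU. A patient at zero on both days would have stayed in the ICU for a week without organ dysfunction. Those who recover and leave may have no D21 score, so the written cases do not cover them. Externally transferred patients have totals entered by the site (SAP 5.3.1, 5.3.3.7). This also stands.

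**Two stronger readings are not supported.** A reader might infer a shortfall of up to 7 days, for zero at D14 and D21 followed by non-zero at D28. Half of that comes from calling the 0% relapse credit an error, when it can be a deliberate conservative choice, and the total also requires seven-day intervals.

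A reader might also infer that the rule compresses any treatment benefit. That is not shown. It applies alike to both arms, the test is rank-based, and the SAP summaries for this endpoint exclude means, so Step 3 concerns a statistic the plan does not report. With equal history to D13 and both zero at D21 and D28, a patient at zero on D14 still ranks above one who is not, because D14 itself counts. Dilution would need a difference between arms in p, for which the documents give no figure.

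**Conclusion.** The point holds in limited form. As written in SAP 5.3.3.3, the rule disregards a score that is already recorded, and it credits the same zero-to-zero pattern at 50% in one interval and 100% in the next. The inconsistency costs an affected patient 3 days, or 3.5 on the seven-day reading. Where D14 is zero and D21 is not, the interval earns nothing; whether that is too little depends on the relapse convention, which the SAP does not explain.

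The consequence is imprecision and possible dilution in one secondary endpoint and one cost item, with no direction between arms. The endpoint lies outside the hierarchies in Protocol 8.5.2.1.1 and SAP 6.1.3. The primary endpoint and the sample size are untouched. The conclusion assumes that the body text reflects the programmed rule. The trial-level size remains unknown because the share of patients at SOFA 0 on D14 and D21 is not given.

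**What to change.** Before the Day 90 database lock, while treatment codes are still blinded:

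1. Define the D14–D21 credit by the scores at both ends: 100% if both are zero, 50% if exactly one is, 0% if neither.
2. State the case where D21 and D28 are both non-zero.
3. For D21–D28, either make recovery and relapse symmetric or keep 50% against 0% and say that it is a deliberate conservative choice. If 0% for relapse is kept, say whether it also applies to D14–D21, so that the two intervals follow one convention.
4. Say whether an interval has six or seven days, and what happens when D14 or D21 is missing after ICU discharge.
5. Make Section 5.9.4.2 of Appendix 4 match.

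Protocol 6.1.2.1 also lists the SOFA component variables as assessed daily to D28 or ICU discharge. If those data exist, days spent in the ICU could be scored directly and the fill-in kept for the rest.

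The cost is a reworded derivation rule and a small programming change. Items 1 to 3 and 5 need no new data, and item 4 needs only a stated convention.
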